3.2.4. Annualized FIX Consumption

Annualized FIX consumption will be reported by IU/kg and total units, and a similar approach of data collection and endpoint derivation as described for AIR will be used. This endpoint of FIX consumption not only measures the number of infusions but also the total units consumed.

3.2.5. Annualized Bleeding Rate of Specific Type of Bleeding

Other secondary endpoints, such as annualized bleeding events (ABR_{total}) of a specific type: by cause: spontaneous, traumatic; by location: in joint (including target joints), in soft tissue, and untreated bleeding, as defined in the Protocol Appendix 7, will be calculated and summarized. The data collection and endpoint derivation are similar to those described for ABR_{total}. The baseline for each specific type of bleeding episode will be derived similarly as defined for ABR_{total}, with baseline of these endpoints obtained from the Pre-Infusion Period. The investigators will assess the health of the joint(s), identified target joints (Section 3.3.1.1) at baseline prior to PF-06838435 infusion. Any bleeding occurring during the study into the identified baseline target joints will be considered as target joint bleeds and will be summarized.

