3.3.1.1. Target Joints

A target joint is defined as a major joint (e.g., hip, elbow, wrist, shoulder, knee, and ankle) into which repeated bleeds occur (three or more spontaneous bleeds into a single joint within a consecutive 6-month period). Investigators will assess the health of the target joint(s), identified at baseline (during screening period of study C0371002) and other visits, as scheduled per SoA. A target joint is considered resolved when there are ≤ 2 bleeds into the joint within a 12-month period. A newly developed target joint is a major joint that is not identified as target joint at baseline, and has three or more spontaneous bleeds within a consecutive 6-month period post PF-06838435 infusion. If prophylaxis FIX regimen is resumed for a participant, then the time period following the resumption of the prophylaxis regimen will be excluded from the identification of target joints. The baseline assessment is based on the closest evaluation prior to PF-06838435 infusion, which is measured during the screening period of Study C0371002.

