4. ANALYSIS SETS (POPULATIONS FOR ANALYSIS)

This study is an open-label, single-arm study. The populations for analyses are outlined in the table below.

Population	Description
Enrolled	All participants who sign the informed consent form (ICF) and meet all inclusion/exclusion criteria
Dosed	All participants enrolled in the study and who received PF-06838435 infusion
Safety	All participants enrolled in the study and who received PF-06838435 infusion, which is the same as dosed population.
Evaluable	All participants enrolled in the study and who received PF-06838435 infusion and have no significant interruption of efficacy measurement.

The Evaluable analysis population listed above would exclude participants with significant interruption of efficacy measurement, or participants who do not have or have not yet completed 15 months of follow up post PF-06838435 infusion. Significant interruption will be assessed after discussion between the investigator and the medical monitor, e.g., if a participant requires a major surgery, this will be a significant interruption of measurement.

In this study, there are also substudies planned, for which the analysis populations are outlined below.

X-ray Substudy	All dosed participants sign the additional ICF for the X-ray substudy and meet all
Analysis Population	inclusion/exclusion criteria, and the participant's joint images have been
	reviewed.
MRI Substudy	All dosed participants who are dosed and sign the additional ICF for the MRI
Analysis Population	substudy and meet all inclusion/exclusion criteria, and the participant's joint
	images have been reviewed following the extended MRI scale with a final score
	combining soft-tissue and osteochondral sub-scores at baseline, and any data
	post-baseline
Vector Shedding	All dosed participants who sign the additional ICF for the Vector Shedding
Substudy Analysis	substudy and meet all inclusion/exclusion criteria, and who have any additional
Population	vector shedding data

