5.1. Hypotheses and Decision Rules

In this study, all hypothesis testing will use a two-sided test, unless specified otherwise.

The primary objective is to demonstrate the efficacy of a single infusion of PF-06838435 in male participants \geq 18 years of age with moderately severe to severe hemophilia B (FIX:C \leq 2%). The primary objective is addressed via the primary endpoint of ABR_{total}.

The hypothesis test of ABR_{total} is noninferiority test of pre- and post treatment with PF-06838435 with a noninferiority margin of 3.

A gatekeeping process will be applied to control multiplicity of testing multiple endpoints at the primary analysis. The subsequent hypothesis testing will only be performed after success on a previous hypothesis test, each test performed at the α defined for the primary analysis (0.05). The analyses cease when a failure occurs. The sequence of gatekeeping process is displayed in Table 2. For the last group of hypothesis tests, we would apply Hochberg (1988) step-up procedure so that the familywise error rate will be controlled under 0.05. Note, only selected endpoints are included in the sequence in the table below.

			Hypothes	is testing ce	eases when	a failure occ	ours		
ABR _{total} non- inferior to FIX prophyla xis regimen#	ABR _{treat} non- inferior to FIX prophylaxis regimen#	AIR superior ity to FIX prophyl axis regimen	Steady state FIX:C >5%*	FIX consump- tion superiority to FIX prophylaxi s regimen	ABR _{treat} superiority to FIX prophylaxi s regimen	ABR _{total} superiority to FIX prophylaxi s regimen	Haem-A- QoL Physical Health domain significantly improved from baseline	HAL Complex Lower extremity Activities compone nt score signifi- cantly improved from baseline	ABR _{total} of specific type (spontaneous , trauma, untreated, in target joints,) non-inferior to FIX prophylaxis regimen, and HJHS (Hochberg step-up method)

Table 2. Sequence of Gatekeeping Process of Multiple Hypothesis Tests

#The upper bound of the confidence interval of the difference in ABR_{total} and ABR_{treat} between pre- and post PF-06838435 will be compared to the NI margin. All other hypothesis tests are 2-sided tests. *Steady state FIX:C will be analyzed using a one-sided, one sample t-test.

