6.2.5. Annualized Bleeding Rate of Specific Type

The ABR_{total} of specific types such as spontaneous bleeding, traumatic bleeding, bleeding in joints, bleeding in soft tissue, and untreated bleeding etc. These endpoints will be analyzed similarly as defined for main analysis of ABR_{total}.

These analyses will be conducted on Dosed population.

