6.3. Other Endpoint(s)

6.3.1. Joint Assessments

6.3.1.1. Target Joints

Number and percentage of participants with 0, 1, 2 or \geq 3 target joints at baseline, during the first 15 months post PF-06838435 infusion, and during the overall follow-up period will be summarized, respectively. Number and percentage of participants who have 0, 1, 2 or \geq 3 baseline target joints resolved during the first 15 months post PF-06838435 infusion, and during the overall follow-up period will be summarized. Similarly, number and percentage of participants who developed new target joints (1, 2 or \geq 3 target joints) during the first 15 months post PF-06838435 infusion, and during the overall follow-up period will be summarized. Similarly, number and percentage of participants who developed new target joints (1, 2 or \geq 3 target joints) during the first 15 months post PF-06838435 infusion, and during the overall follow-up period will be summarized. The number and location of target joints at baseline and post PF-06838435 infusion will be provided in a data listing.

The Dosed population will be used for this analysis.

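### Target-joint bleed rates and resolution percentages use the whole Dosed population, although only participants with a baseline target joint can contribute events

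*SAP*

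**What the plan says.** SAP 3.3.1.1 defines a target joint as a major joint with "three or more spontaneous bleeds into a single joint within a consecutive 6-month period", and treats joints that first meet this after infusion as a separate, newly developed category. SAP 3.2.5 ties the bleed endpoint to the baseline set: "Any bleeding occurring during the study into the identified baseline target joints will be considered as target joint bleeds".

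SAP 6.2.5 covers bleeds of specific type. It sends the reader to the main analysis of total ABR and adds: "These analyses will be conducted on Dosed population". Its list of types ends in an 'etc.' and does not name target joints. However, 3.2.5 places them in this family, Protocol 9.4.1 applies the total-ABR method to them, and SAP 5 makes Dosed the default. Dosed means "All participants enrolled in the study and who received PF-06838435 infusion" (SAP 4).

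SAP 5.1, Table 2, places the endpoint in the last, Hochberg-adjusted group of the hierarchy, as a test of being "untreated, in target joints,) non-inferior to FIX prophylaxis regimen". Table 2 gives no margin for it.

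SAP 6.3.1.1 tabulates participants by number of target joints at baseline, number of baseline target joints resolved, and number newly developed, and says: "The Dosed population will be used for this analysis". It names no separate denominator for resolution. SAP 6.4 plans no subset analysis.

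**The concern.** A participant without a baseline target joint cannot have this event in either period, yet supplies person-time to both. In a superiority setting those structural zeros would make an absolute benefit look smaller. In a non-inferiority test on an absolute difference they work the other way: they pull a harmful difference toward zero and make it easier to stay below a fixed margin. A worsening confined to participants who have target joints could then pass.

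The resolution table has a related fault. Its zero-resolved row combines participants who had nothing to resolve with participants whose target joint did not resolve, and these are different outcomes.

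**Working it through.** **Figures in the plan.** The documents give no target-joint prevalence, target-joint bleed rate or margin specific to this endpoint, so there is no figure to reproduce. The stated power of at least 90% (Protocol 9.2) concerns total ABR and does not bear on this point.

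**Inputs.**
- N = 40 and a margin of 3.0 bleeds/year: Protocol 9.2. Applying 3.0 here is an inference from SAP 6.2.5.
- Post-infusion period: Day 82 to Day 469 (SAP 5.2), so (469 − 82 + 1)/365.25 = 388/365.25 = 1.06 years.
- Pre-infusion period: at least 0.5 year (SAP 6.1.1.1).
- p: not given, so varied.

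**Step 1, dilution.** Assume similar person-time in participants with and without a baseline target joint. Let the at-risk rates be a (pre) and b (post).
- Dosed rates: p·a and p·b
- Dosed difference: p·(b − a)
- Dosed percentage with at least one joint resolved: p × the at-risk percentage
- Dosed ratio: p·b/(p·a) = b/a, unchanged
- At-risk difference equivalent to a Dosed margin of 3.0: 3.0/p

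The last two columns use an illustration with assumed at-risk rates of 4 falling to 1 (difference −3, ratio 0.25) and 80% resolved.

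| p | n of 40 | dilution 1/p | 3.0/p | Dosed difference | Dosed % resolved |
|---|---|---|---|---|---|
| 0.20 | 8 | 5.00 | 15.0 | −0.60 | 16% |
| 0.25 | 10 | 4.00 | 12.0 | −0.75 | 20% |
| 0.50 | 20 | 2.00 | 6.0 | −1.50 | 40% |
| 0.75 | 30 | 1.33 | 4.0 | −2.25 | 60% |
| 1.00 | 40 | 1.00 | 3.0 | −3.00 | 80% |

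**Step 2, the non-inferiority decision.** Suppose bleeds among those at risk truly rise from 3 to 6 per year. Counts are Poisson with gamma heterogeneity (dispersion k = 1, shared across periods), exposures are 0.5 and 1.06 years, and the test passes if the upper limit of a two-sided 95% paired t interval is below 3.0. In 20,000 runs the test passed as follows.

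| p | Dosed | At risk only |
|---|---|---|
| 0.25 | 97.8% | 7.7% |
| 0.50 | 71.8% | 6.3% |
| 0.75 | 27.3% | 5.2% |
| 1.00 | 5.0% | 5.0% |

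I then varied k from 0.25 to 2, used shared or independent participant effects, and set pre-infusion exposure at 0.5 or 1.0 year. The Dosed pass rate ranged over about 67–99.7% at p = 0.30, 37–89% at p = 0.50 and 15–34% at p = 0.75. The at-risk pass rate stayed between about 3% and 12%.

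**Step 3, population or margin?** At p = 0.30 with k = 1 and 0.5 year pre-infusion, Dosed passes in 95.6% of runs against 3.0. Scaling the margin to 0.30 × 3.0 = 0.9 brings this down to 7.4%, against 7.2% in the at-risk set with 3.0. The effect therefore comes from pairing an unscaled margin with a population that includes participants not at risk.

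**The case against.** The Dosed mean is a legitimate quantity. It is the number of target-joint bleeds per treated participant, and it matches the population of the primary estimand (SAP 2.1.1). It is not a biased estimate of the at-risk rate; it answers a different question. This stands, and so does the fact that the pre/post ratio is identical in both sets. But the planned test uses the difference: SAP 6.2.5 points to the identity-link main analysis, not to the supportive log-link model.

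Step 3 supports a second objection, that the missing margin matters as much as the population. This stands too, so the fix must state a margin.

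Third, the scenario in Step 2 sets the at-risk difference exactly at the margin, uses a paired t interval instead of the SAP's negative binomial model, and treats one test in isolation. In Table 2 the group is reached only after nine earlier successes, including superiority on treated and total bleeds. A reader might infer that a doubling of target-joint bleeds would almost always be declared non-inferior in this trial. The documents do not support that: the pass rate depends heavily on p and on the heterogeneity, and the hierarchy is not modelled.

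Fourth, the resolution figure is partly recoverable, because SAP 6.3.1.1 also tabulates participants by number of target joints at baseline and lists the joints. With 12 of 40 having a target joint and 9 resolving at least one, a reader could turn 9/40 = 22.5% into 9/12 = 75%. The mixed zero-resolved row remains unclear, and the test result cannot be converted in this way.

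**Conclusion.** The point holds as a matter of definition and arithmetic. Absolute rates, absolute differences and the percentage with at least one joint resolved are scaled by p, and a fixed margin on Dosed is 1/p times as lenient for the participants the endpoint concerns. The size is conditional. A reader might infer that the dilution is several-fold, but it reaches 3-fold only if p is at most one third (about 13 of 40), and no document gives p. The leniency also rests on the 3.0 margin carrying over to this endpoint, which the SAP implies but does not state.

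The endpoint sits in the last testing group and the number of target joints is exploratory, so the primary and key secondary conclusions do not change. It is still worth correcting, because the error favours the non-inferiority claim and no planned analysis restricts the comparison to participants at risk.

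**What to change.** In SAP 6.2.5, name target-joint bleeds explicitly. Run their comparison on dosed participants with at least one baseline target joint, using only those participants' person-time. Report n, and state and justify the margin for this endpoint. Keep the Dosed version as supportive.

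In SAP 6.3.1.1, use the same participants as the denominator for resolution, and add a joint-level count of resolved joints over baseline target joints. Keep the full Dosed denominator for newly developed target joints, since any participant can develop one. The SAP already restricts a denominator in this way for corticosteroid dose escalation (SAP 6.6.2).

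The cost is SAP wording and one subset flag. The price is a smaller n, a wider interval and possible instability of the identity-link negative binomial model in a small set, so a fallback method should be named in advance.

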3.2.6. Percentage of Participants Without Bleeds

The percentage of participants without bleeds will be determined for the overall time period, running total (i.e., Week 12 to Month 15, Week 12 to Year 2, Week 12 to Year 3, etc.) and

Week 12 to Month 15, Month 15 to Month 24 (Year 2), and yearly intervals after Month 24. The percentage of participants without bleeding at baseline will be obtained from Pre-Infusion Period, and will also be summarized.

3.2.7. Hemophilia Joint Health Score (HJHS)

A qualified healthcare professional will assess joints to derive modified HJHS, adapted from the original joint scoring system [1]. Six joints (left ankle, right ankle, left elbow, right elbow, left knee, right knee) will be scored on a scale from 0 to 20 according to the following criteria: duration of swelling, muscle atrophy, crepitus, flexion loss, extension loss, instability, joint pain, and strength. Gait will be scored on a scale from 0 to 4 based on walking, stairs, running, hopping on one leg. The total score will be the sum of scores from all joints plus the gait score (range from 0 to 124), with the higher the number equating to more severe joint damage. The HJHS total score is obtained using the following formula excluding the not evaluable (NE) items:

 $HJHS \text{ Total Score} = \frac{\text{total score of evaluated items (excluding NE's)}}{\text{possible maximum total score of evaluated items (excluding NE's)}} \times 124$

HJHS Total Score will not be derived if >20% of items are missing (including NE items). Note: there are 49 individual items to score, therefore 10 or more missing or NE will result in the total score not being calculated.

The baseline assessment is based on the latest evaluation prior to or on the day of PF-06838435 infusion, which is measured during the screening period of Study C0371002.

3.2.8. Patient-Reported Outcome Assessments

PROs should be completed as per SoA using an electronic tablet provided to each site.

3.2.8.1. Haemophilia Quality of Life Questionnaire for Adults (Haem-A-QoL)

The Haem-A-QoL Questionnaire is designed for adult (\geq 17 years) patients with hemophilia. It contains 46 items with ten domains that assess health in the following areas: Physical Health (5 items); Feelings (4 items); View of Self (5 items); Sports and Leisure (5 items); Work and School (4 items); Dealing with Haemophilia (3 items); Treatment (8 items); Future (5 items); Family Planning (4 items); and Partnership and Sexuality (3 items). The total score is also considered.

Each item has a response on the 5-point Likert Scale ranging from "Never" to "All of the time" with several items having a "not applicable" option.

The items prompt the responder to consider life in the last four weeks ("four-week recall"). The items are self-explanatory and the questionnaire can be completed in about 15 minutes.

Scoring is performed by averaging the non-missing item responses for each domain, and then rescaled to be on 0 to 100, with lower scores representing higher quality of life. The total score is directly averaged across the 46 items values and then rescaled on zero to 100.

A domain score can be calculated if \geq 50% of that domain's items have been answered.

There is an expectation that the questionnaire is being administered electronically and designed such that patients are not able to skip items. That is, there should not be any missing items unless the participant does not complete the questionnaire.

The Physical Health domain is considered as the primary domain in this questionnaire and is a secondary endpoint, and will be further assessed using the anchor-based method for each yearly visit.

3.2.8.2. Hemophilia Activities List (HAL, v2)

The Hemophilia Activities List (version 2) is a multiple domain measure of the impact of hemophilia on functional abilities in adults. The 7 domains of this instrument contain 42 items in total, as follows: Lying/sitting/kneeling/standing (8); Lower (leg) functioning (9); Upper (arm) functioning (4); Transportation (3); Self-care (5); Household tasks (6); and Sports/Leisure (7). An overall sum score and three component scores can be calculated along with individual domain scores.

All individual items are rated on a 6-point scale from 1 (impossible) to 6 (never) describing difficulty due to hemophilia in the past month. Several items allow the respondent to mark as "not applicable."

Selected items from five of the domains are used to create three components: upper extremity; basic lower extremity; and complex lower extremity activities.

Responses from individual items can be summed to give a score for each domain and component, and the total. Higher values indicate better quality of life, that is, higher values indicate less functional limitations in performing tasks.

The activities list also includes two sets of multiple-choice items assessing the use of adaptive and assistive devices; these items are not included in the scoring.

Each domain or component, or the total, must have a minimum number of valid responses or the score is set to missing. An implication of the "minimum number of valid responses" is that there is an acceptable amount of missing data where the scores (domains, components, and total; score and normalized score) can still be calculated.

The component score of "complex lower extremity activities" is considered the most important in this questionnaire and is a secondary endpoint, and will be assessed using the anchor-based method for each yearly visit. Hemophilia Activities List baseline is the closest evaluation prior to or on the day of PF-06838435 infusion, which is measured during the screening period of Study C0371002. The normalization method to derive score of domains and three components will be used to impute any missing item.

3.2.9. Immunogenicity

Peripheral blood mononuclear cells (PBMCs) result by Interferon gamma (IFN- γ) enzymelinked immunosorbent spot (ELISPOT) to assess cellular immune responses to AAV capsid, FIX, R338L, and other peptide pools will be presented in a summary table.

Anti-Drug antibody (ADA) and neutralizing antibody (nAb) to AAV capsid results from the central lab will be collected according to the SoA.

FIX Inhibitor results by Bethesda Assay will be collected throughout the study and reported.

3.3. Other Endpoint(s)

3.3.1. Joint Assessments

Joint health will be assessed via multiple methods in this study. In general, missing data will not be imputed for joint assessment results.

3.3.1.1. Target Joints

A target joint is defined as a major joint (e.g., hip, elbow, wrist, shoulder, knee, and ankle) into which repeated bleeds occur (three or more spontaneous bleeds into a single joint within a consecutive 6-month period). Investigators will assess the health of the target joint(s), identified at baseline (during screening period of study C0371002) and other visits, as scheduled per SoA. A target joint is considered resolved when there are ≤ 2 bleeds into the joint within a 12-month period. A newly developed target joint is a major joint that is not identified as target joint at baseline, and has three or more spontaneous bleeds within a consecutive 6-month period post PF-06838435 infusion. If prophylaxis FIX regimen is resumed for a participant, then the time period following the resumption of the prophylaxis regimen will be excluded from the identification of target joints. The baseline assessment is based on the closest evaluation prior to PF-06838435 infusion, which is measured during the screening period of Study C0371002.

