### 6.5.1. Allowed Therapy

During the study participants are requested to suspend their FIX prophylaxis regimen after infusion of PF-06838435, but may take:

- FIX replacement therapy is allowed, as needed. The infusion data (specific product, date, time, dosage, reason) is to be recorded in the eDiary.
- For a bleeding event, the investigator / study staff will recommend the appropriate dose of FIX to treat the bleed because the dose of factor concentrate should include the recent steady-state PF-06838435 induced FIX activity levels to avoid overdosing resulting in a potential thrombotic event. The table in [Appendix 8](#) provides guidelines for target FIX levels based on bleed type.
- A participant may resume prophylaxis if the PF-06838435 treatment is not efficacious, defined for this study as:
  - FIX activity after 12 weeks of  $\leq 2\%$  (in the absence of a confirmed FIX inhibitor) as determined by the central laboratory on 2 consecutive samples collected within a 2 week period;and/or
  - Over a 4-week period (in the absence of a confirmed FIX inhibitor);
    - 2 or more spontaneous bleeds into a major joint and/or target joint;or
    - 3 or more spontaneous bleeds (consisting of joint bleeds and/or significant soft tissue/muscle or other site bleeds). Significant spontaneous bleeds are defined as those that lead to a transient or persistent loss of function.

The investigator is to discuss the case with the sponsor's medical monitor prior to resumption of prophylaxis. Dosing of prophylaxis will take into account the current steady-state FIX activity level. A participant who resumes prophylaxis may choose to discontinue it; however, prior to discontinuation, the investigator is to discuss with the sponsor's medical monitor.

Additional allowed therapies include the following:

- COX-2 inhibitors and topical NSAIDs, where medically necessary
- HIV therapy

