### **Definition of a Bleed Location**

Target Joint: Defined as a major joint (eg, hip, elbow, wrist, shoulder, knee, and ankle) into which repeated bleeds occur (three or more spontaneous bleeds into a single joint within a consecutive 6-month period). A target joint is considered resolved when there are  $\leq 2$  bleeds into the joint within a 12-month period.

Joint Bleed: A bleeding episode characterized by rapid loss of range of motion as compared with baseline that is associated with any combination of the following: pain or an unusual sensation in the joint, palpable swelling, and warmth of the skin over the joint.

Muscle Bleed: An episode of bleeding into a muscle, determined clinically and/or by imaging studies, generally associated with pain and/or swelling and functional impairment.

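### SAP 3.3.1.1 excludes time after prophylaxis resumption from identifying target joints but not from resolving them, so a joint that is quiet on resumed FIX could be counted as resolved

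*SAP*

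**What the plan says.** SAP 3.3.1.1 sets three rules and one exclusion:

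- **Resolution:** "A target joint is considered resolved when there are ≤ 2 bleeds into the joint within a 12-month period". Protocol 8.1.2 and Appendix 7 use the same threshold, also without a condition on prophylaxis.
- **New target joint:** a major joint that was not a target joint at baseline and "has three or more spontaneous bleeds within a consecutive 6-month period post PF-06838435 infusion".
- **Exclusion:** if prophylaxis is resumed, "then the time period following the resumption of the prophylaxis regimen will be excluded from the identification of target joints".

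SAP 6.3.1.1 then tabulates participants by number of "baseline target joints resolved during the first 15 months post PF-06838435 infusion, and during the overall follow-up period will be summarized". New target joints are tabulated for the same two periods. On the analysis set it says "The Dosed population will be used for this analysis", so participants who resume stay in the table.

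Protocol 6.5.1 defines who these participants are: "A participant may resume prophylaxis if the PF-06838435 treatment is not efficacious, defined for this study as" either low FIX activity after 12 weeks or a cluster of spontaneous bleeds within 4 weeks. Under Protocol 8.1.1 their bleeds continue to be reported throughout the study, so the data needed to apply the resolution rule after resumption will exist.

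**The concern.** Acquiring a target joint is the unfavourable outcome and resolving one is the favourable outcome. The stated exclusion removes post-resumption time only from the first. A joint that bleeds little once regular FIX has been restarted says something about FIX prophylaxis, not about the vector. Yet the text allows it to be shown as resolved after gene therapy.

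This also sits awkwardly with the reasoning in SAP 2.1.1, where data after resumption are dropped from the primary analysis because they no longer describe the efficacy of the study treatment. SAP 3.1.1 carries that through for ABR by removing both the bleeds and the observation time. At stake is a durability statement: how many baseline target joints resolved over up to 6 years.

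**Working it through.** The plan states no figure for this count, so there is none to reproduce. The check has four parts.

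**1. Does another section close the gap?**

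| Place | Handling of time after resumption |
|---|---|
| SAP 3.1.1 (ABR) | Bleeds and time both removed |
| SAP 2.1.2.5 | ABR handling extended to target joint bleed frequency and percentage without bleeds; resolution not named |
| SAP 3.3.1.1 | Removed from identification; resolution not named |
| SAP 6.3.1.1 | Resolution tabulated; no exclusion stated |
| Protocol 8.1.2, Appendix 7 | Resolution defined; no exclusion stated |

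None of these sections closes it.

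**2. Can the two rules collide without any rate assumption?** One resumption trigger in Protocol 6.5.1 is 2 or more spontaneous bleeds into a major or target joint within 4 weeks. Take exactly 2 such bleeds into a baseline target joint, then resumption, then none. A 12-month window that includes the failure holds 2 bleeds, and 2 ≤ 2, so the joint meets the resolution rule.

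**3. Which table is exposed?** A 12-month window wholly after resumption must end inside the reporting period.
- Overall follow-up: 72 − 12 = 60, so resumption up to about Month 60 leaves room.
- First 15 months: 15 − 12 = 3, so resumption is needed by about Month 3. If the period closes at Day 469, as for ABR, the limit is 469 − 365 = Day 104. The FIX-activity trigger applies only after 12 weeks (12 × 7 = Day 84), which leaves about 20 days for that route.
- Windows that straddle resumption can qualify in the 15-month table with later resumption, but they must absorb the bleeds before it.

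**4. How likely is a quiet window?** The documents give no per-joint rate on resumed prophylaxis, so the rate r (bleeds per year) is assumed. With a constant Poisson rate, P(at most 2 in 12 months) = exp(−r) × (1 + r + r²/2).

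| r | Calculation | P |
|---|---|---|
| 1 | 0.3679 × 2.5 | 0.92 |
| 2 | 0.1353 × 5 | 0.68 |
| 3 | 0.0498 × 8.5 | 0.42 |
| 5 | 0.00674 × 18.5 | 0.12 |
| 6 | 0.00248 × 25 | 0.06 |

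The upper end has an anchor in the definition: 3 spontaneous bleeds in 6 months is 3 × 2 = 6 per year. The resumption trigger of 2 in 4 weeks is 2 × 52/4 = 26 per year, where P is about 0.

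These are single-window figures. The rule asks only for some 12-month period, and long follow-up offers several. With five non-overlapping windows (resumption by about Month 12), the chance that at least one qualifies is 1 − (1 − 0.42)^5 ≈ 0.94 at 3 per year and 1 − (1 − 0.06)^5 ≈ 0.27 at 6 per year, under the same constant-rate assumption.

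**The case against.** The strongest reply is that this is silence, not a rule. No section says that post-resumption time counts toward resolution. The exclusion sentence follows all three definitions and could be read as covering target joint status in general, since a resolved joint is one no longer identified as a target joint. Target joint bleed frequency already follows the ABR handling, and resolution counts bleeds into the same joints.

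That reading is possible, but the text does not require it: identification, resolution and new development are defined separately, and the exclusion names only one. Borrowing the ABR bleed set is also safe only if the time is removed too. Dropping the bleeds but keeping the calendar window would make resolution easier.

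Three stronger inferences are tempting, and the documents do not support them:
- **That most resumers' target joints would be scored as resolved.** This needs about 1 to 2 bleeds per year into the joint. Participants were on prophylaxis for at least 6 months before infusion, so a target joint that qualified in that period bled at about 6 per year while on prophylaxis, where P is 0.06. Some target joints come from the hemophilia history and may be older, so lower rates are possible too. The direction is clear but the size is not.
- **That the count will be overstated.** It could be, if programmed literally.
- **That the rule breaches an estimand.** The reason in SAP 2.1.1 belongs to the ABR estimand. None is defined for resolution, and handling differs by endpoint: AIR deliberately keeps infusions after resumption.

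It is also fair that the harm is small and partly visible. SAP 6.3.1.1 lists target joints, and SAP 6.2.2.2 reports the percentage resuming by interval.

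**Conclusion.** The point holds as a one-sided gap in the written rules. Followed literally, SAP 3.3.1.1 blocks new target joints after resumption but leaves resolution open, and no other section corrects this. The resolved count could be overstated by an amount that cannot be fixed from the documents: 0.92 down to 0.06 per affected joint and window, under assumed constant Poisson rates of 1 to 6 per year. The exposure is mainly in the overall follow-up table.

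The importance is low. Number of target joints is tertiary/exploratory, and resolution is a descriptive count outside the testing sequence in SAP Table 2. Only participants who both have a baseline target joint and resume prophylaxis are affected, and the documents forecast neither number. With 40 in the Dosed population as denominator, each such participant moves a percentage by 1/40 = 2.5 points. The primary and key secondary conclusions do not depend on it.

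**What to change.** In SAP 3.3.1.1, extend the existing exclusion so that time after resumption of prophylaxis is left out of both the identification and the resolution of target joints. Mirror this in SAP 6.3.1.1. State that a joint which already met the 12-month rule before resumption stays resolved. Show baseline target joints with less than 12 months of observation before resumption in a separate row, labelled not assessable or not resolved, with the choice made before database lock.

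The extra row goes a little beyond closing the ambiguity, but some classification is unavoidable once the time is excluded, because these joints cannot complete a 12-month window.

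The cost is one sentence, one cross-reference and one table row. No new data are needed and patient management is unchanged. The resolved count can only stay the same or fall, because the change removes qualifying windows and adds none.
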